**Provider Notes:**

**Provider Signature and Printed Name/Stamp:**

Last Name

First Name

MI

Social Security Number

Patient's identification (May use mechanical imprint)

RECORDS MAINTAINED AT:  
 RANK/GRADE  
 SEX  
 DATE OF BIRTH  
 SPONSOR NAME  
 (or Sponsor SSN)  
 RELATIONSHIP TO SPONSOR  
 (Or FMP)  
 ORGANIZATION  
 STATUS  
 DEPT/SVC

CHRONOLOGICAL RECORD OF MEDICAL CARE  
**Smallpox Vaccination Continuation Note**

1. Today's Date (MM/DD/YYYY)

□□ / □□ / □□□□

Additional Notes on Problems, Issues or Concerns of Patient or Provider related to Vaccine Assessment or Follow-up. Subjective section may be filled out by either patient/vaccine or provider. Objective findings, Assessment and Plan should be completed by a provider.

Subjective: History of issues related to vaccination assessment or follow-up

[Empty box for Subjective notes]

Objective: Relevant exam, test or laboratory findings

[Empty box for Objective findings]

Assessment: Integrated summary

[Empty box for Assessment]

Plan

[Empty box for Plan]

Provider Signature and Printed Name/Stamp:

[Empty box for Provider Signature and Printed Name/Stamp]

Last Name

□□□□□□□□□□□□□□□□

First Name

□□□□□□□□□□

MI

□

Social Security Number

□□□ □□□ □□□□□□

Patient's identification (May use mechanical imprint)

- RECORDS MAINTAINED AT:
- RANK/GRADE
- SEX
- DATE OF BIRTH
- SPONSOR NAME (or Sponsor SSN)
- RELATIONSHIP TO SPONSOR (Or FMP)
- ORGANIZATION
- STATUS
- DEPT/SVC

### Symptom Diary After Smallpox Vaccination

- a) Patient name: Last \_\_\_\_\_ First \_\_\_\_\_ MI \_\_\_\_\_      b) Social Security Number: \_\_\_\_\_ - \_\_\_\_\_ - \_\_\_\_\_
- c) Date of Birth: Mo \_\_\_\_/Day \_\_\_\_/Yr \_\_\_\_      d) Age: \_\_\_\_ years      e) Gender:  Male  Female
- f) Date of smallpox vaccine administration: Mo \_\_\_\_/Day \_\_\_\_/Yr \_\_\_\_      g) Clinic / site where vaccination was given: \_\_\_\_\_
- h) Taken any steroids/pain/fever medications:  1-3 days before vaccine(\_\_\_\_\_)  0-30 days after vaccine(\_\_\_\_\_)  None during this period (-3 to +30 days)
- i) Ethnicity  White/Caucasian  Asian  Black/African American  Native Hawaiian/Other Pacific Islander  
 Hispanic  American Indian/Alaskan Native  Do not want to provide  Other (specify: \_\_\_\_\_)

THE FIRST 4 WEEKS AFTER SMALLPOX VACCINATION: Please check any symptoms present on each indicated day recording details below	Day 0 vaccination)	Day 1	Day 2	Day 3	Day 4	Day 5	Day 6	Day 7	Day 8	Day 9	Day 10	Day 11	Day 12	Day 13	Day 14	Day 15	Day 16	Day 17	Day 18	Day 19	Day 20	Week 4
1. Symptoms (Y or N)																						
2. Fever (record temperature, eg.101.2F)																						
3. Chills (Y or N)																						
4. Swelling at vaccination site (Y or N)																						
5. Cough/ difficulty breathing (Y or N)																						
6. Rash or vaccine-type reaction on body (Y or N, if Y describe rash and where, below)																						
7. Bandage used (Y or N, type below)																						
8. Did you seek medical care because of vaccination? (describe below)																						
9. Did you take any medications because of vaccination?(specify below)																						
10. Did you miss work/school because of vaccination?																						
11. Joint pain (0-9scale) (0=no, 9=worse)																						
12. Muscle pain (0-9 scale)																						
13. Headache (0-9 scale)																						
14. Pain at vaccination site (0-9 scale)																						
15. Swelling/tender lymph nodes (0-9 scale)																						
16. Itching at vaccination site (0-9 scale)																						
17. Chest pain (0-9 scale)																						
18. Shortness of breath (0-9 scale)																						
19. Other symptoms, illnesses, new medications, etc.(describe below)																						
20. Vaccination site appearance (using letter codes below)																						

**Date scab fell off: Mo \_\_\_\_/Day \_\_\_\_/Yr \_\_\_\_**      **If at any time you have questions about your vaccination please contact the DoD Vaccine Clinical Call Center at [name] (24 hrs a day, 7 days a week) or email the Vaccine Healthcare Center at <https://askvhc.wranc.amedd.army.mil>**

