### 4.5 Trial Halting Rules

A temporary halting or termination for the trial as a whole can be decided by the DSMB in the event of an occurrence of

- an SAE
- an unexpected Grade 3 or higher systemic reaction or lab toxicity ([Appendix I; Section 17.1](#))

with an at least reasonable possibility of a causal relationship to the administration of MVA-BN®, i.e. the relationship cannot be ruled out.

Suspected cases of illnesses such as progressive vaccinia, eczema vaccinatum, and severe generalized vaccinia or inadvertent inoculation or other SAE observed after smallpox vaccination with ACAM2000® should be reported immediately following standard of practice. VIG and Cidofovir are available from CDC for treatment of AEs among smallpox vaccine recipients and their contacts under IND protocols.

Additionally, SAEs after ACAM2000® vaccination should be reported to the Vaccine Adverse Event Reporting System (VAERS). Reports can be submitted through a secure Internet-based system at <https://vaers.hhs.gov/esub/step1>. Printable VAERS forms are located online at

[https://vaers.hhs.gov/resources/vaers\\_form.pdf](https://vaers.hhs.gov/resources/vaers_form.pdf), or postage-paid forms can be obtained by calling [name] (toll-free). Submission of VAERS reports by Internet is encouraged to expedite processing and data entry. Completed forms can be faxed to [name] (toll-free) or mailed to [name]. Additional information related to VAERS reporting can be obtained by calling [name] or by e-mail at [[contact]](mailto:[contact]).

These parameters are not all-inclusive. Other AEs could occur that would trigger a DSMB review. Any member of the DSMB, the PI and/or the BN Pharmacovigilance Officer could request a DSMB review based on any observation.

If an event fulfilling the trial halting criteria reaches the investigator's attention, the investigator has the responsibility to alert the responsible DS Department immediately (within 24 hours) and provide a comprehensive documentation of the event. Contact details of the responsible DS Department are provided in [Section 8.3.1](#).

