#### **8.1.3.2 Solicited Adverse Events**

Within this CTP solicited AEs are defined as all symptoms specifically listed in the memory aid provided to the subjects following each vaccination. The subjects are requested to monitor and record local symptoms (i.e. pain, redness (erythema), swelling, induration, itching (pruritus) and

vaccination site appearance (normal/healed, red spot, bump, reddish blister, whitish blister, scab, ulcer/crater, warmth, swollen >3in, red streaks, drainage) as well as general symptoms (i.e. body temperature, headache, muscle pain (myalgia), chills, nausea, fatigue, malaise, swollen lymphnodes) in the memory aid daily for the day of vaccination and the following 14 days (days 0-14, 15 day period). Any symptoms persisting beyond Day 14 post vaccination are recorded in a memory aid extension. The definition of AEs originates from the MVA-BN® Investigator's Brochure and the ACAM2000® Prescribing Information ([Appendix IVc](#); [Section 17.7](#)).

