#### Assessment of Intensity

Injection site erythema	size measured in diameter
Injection site swelling	size measured in diameter
Injection site induration	size measured in diameter

The maximum severity will be scored as follows:

0	=	0
1	=	< 30 mm
2	=	≥ 30 – <100 mm
3	=	≥ 100 mm

Injection site pruritus:

0	=	No symptoms
1	=	Mild: routine daily activities not impaired
2	=	Moderate: routine daily activities impaired
3	=	Severe: prevents routine daily activities

Injection site pain:

- 0 = No pain
- 1 = Pain when touched
- 2 = Pain when moving the limb
- 3 = Spontaneously painful

For red spot, bump, reddish blister, whitish blister, scabs, ulcers/craters, warmth, swollen > 3 in., red streaks or drainage the presence or absence of the symptom is captured in the memory aid. The injection site pruritus and injection site pain is rated by the subject in the memory aid.

Assessment of Causality

Solicited local AEs are defined as being related to the vaccine.

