vaccinia-naïve subjects and <1% of previously vaccinated subjects. Other adverse events included back pain, arthralgia and pain in extremity and none occurred with a frequency of more than 2% in either the vaccinia-naïve or previously vaccinated populations.

- **Blood and Lymphatic System Disorders:** The only adverse event occurring at ≥5% in the ACAM2000 studies were lymph node pain and lymphadenopathy. The incidence of severe lymph node pain and lymphadenopathy was <1%.
- **Gastrointestinal (GI) Disorders:** Commonly reported GI disorders among ACAM2000-treated subjects included nausea and diarrhea (14%), constipation (6%), and vomiting (4%). Severe abdominal pain, nausea, vomiting, constipation diarrhea and toothache accounted for all the severe adverse events reported and occurred in <1% of subjects.
- **Skin and Subcutaneous Tissue Disorders:** Erythema and rash were noted in 18% and 8% of subjects respectively. In ACAM2000 subjects 1% of vaccinia-naïve and <1% of previously vaccinated subjects experienced at least one severe adverse event. With the exception of one case of contact dermatitis and one case of urticaria, erythema and rash accounted for all severe events.

Generalized rashes (erythematous, papulovesicular, urticarial, folliculitis, nonspecific) are not uncommon following smallpox vaccination and are presumed to be hypersensitivity reactions occurring among persons without underlying illnesses. These rashes are generally self-limited and require little or no therapy, except among patients whose conditions appear to be toxic or who have serious underlying illnesses.

Inadvertent inoculation at other body sites is the most frequent complication of vaccinia vaccination, usually resulting from autoinoculation of the vaccine virus transferred from the site of vaccination. The most common sites involved are the face, nose, mouth, lips, genitalia and anus. Accidental infection of the eye (ocular vaccinia) may result in ocular complications including, but not limited to, keratitis, corneal scarring and blindness.

Major cutaneous reactions at the site of inoculation, characterized by large area of erythema and induration and streaking inflammation of draining lymphatics may resemble cellulitis. Benign and malignant lesions have been reported to occur at the smallpox vaccination site.

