a Event was listed on a checklist included in subject diaries; therefore should be considered solicited. In addition to events listed above the following were also included as part of the checklist: chest pain and heart palpitations, but these events did not occur in ≥5% of subjects.

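### The memory aid has no item for rash or lesions away from the vaccination site, so rash in the reactogenicity comparison rests on an open question at visits and may be undercounted

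*Protocol*

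**What the plan says.** Protocol 8.1.3.2 makes the solicited list a closed one: "solicited AEs are defined as all symptoms specifically listed in the memory aid provided to the subjects following each vaccination". The general items are "body temperature, headache, muscle pain (myalgia), chills, nausea, fatigue, malaise, swollen lymphnodes". The local items are pain, redness, swelling, induration and itching, plus the appearance of the vaccination site. Under the local-event grading in 8.2.6.1 the lesion-type items are recorded as present or absent at that site: "For red spot, bump, reddish blister, whitish blister, scabs, ulcers/craters, warmth, swollen > 3 in., red streaks or drainage the presence or absence". The same lists appear in the synopsis, Protocol 9.3.2, and SAP 1.4.4 and 3.9.2. None has an item for rash or for a lesion elsewhere on the body. SAP 3.8.2 classes any event outside the solicited definition as unsolicited.

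Protocol 8.1.3.2 gives the MVA-BN Investigator's Brochure and the ACAM2000 prescribing information as the origin of its adverse event definitions. In Table 3 of that prescribing information (Appendix IVc), rash carries the footnote "Event was listed on a checklist included in subject diaries; therefore should be considered solicited". The diary in Appendix IVd has item 6, "Rash or vaccine-type reaction on body (Y or N, if Y describe rash and where, below", with daily columns for Days 0 to 20 and one for Week 4. The military follow-up notes in the same appendix include a tick box for body rash.

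**The concern.** Comparing the reactogenicity of MVA-BN, ACAM2000 alone and ACAM2000 after MVA-BN is a stated secondary objective (Protocol 3.2). Rash is one of the events on which the vaccines should differ. Protocol Table 1 lists it as uncommon after MVA-BN, and the ACAM2000 label gives about 11% in naïve subjects.

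An event asked about daily by name is usually recorded more completely than one that has to come out of a general question a week or two later. The memory aid also appears to draw on the military diary. Its site-appearance terms (spot, bump, two kinds of blister, scab, ulcer, warmth, swelling over 3 inches, streaks, drainage) correspond to the code key for item 20 of that diary, but item 6 was not carried over and no reason is given.

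What is at stake is the completeness of one descriptive safety rate, and whether it can be set beside the label's diary-solicited figure.

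**Working it through.** **Label figures reproduced (Appendix IVc, Table 3 and section 6.1)**
- Naïve recipients: 94/873 = 10.8%, printed as 11%. Clopper-Pearson 95% interval: 8.8% to 13.0%.
- Previously vaccinated recipients: 80/1,371 = 5.8%, printed as 6%.
- Pooled: (94 + 80)/(873 + 1,371) = 174/2,244 = 7.8%, matching the 8% in section 6.1.

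**Expected rash in Group 2 (220 subjects)**
- 220 × 0.1077 = 23.7, about 24. Over the interval for the rate: 220 × 0.088 to 220 × 0.130, about 19 to 29.

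**Recorded rash under incomplete capture.** The capture fractions are assumptions.

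| Capture | Recorded in Group 2 | Recorded rate |
|---|---|---|
| 100% | 23.7 | 10.8% |
| 75% | 17.8 | 8.1% |
| 50% | 11.8 | 5.4% |
| 25% | 5.9 | 2.7% |

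At 50% capture, the naïve recipients' recorded rate (5.4%) would look like the label's solicited rate in previously vaccinated people (5.8%). That shows how a recorded rate could mislead when set against the label.

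**MVA-BN contrast.** Uncommon in Protocol Table 1 means at least 1/1,000 and below 1/100, so between 220 × 0.001 = 0.2 and 220 × 0.01 = 2.2 subjects. With equal capture of 50% the contrast would be 5.4% against less than 0.5%. The direction would still show, but the size would be understated.

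**Rare vaccinia complications.** Expected cases = 440 × rate; P(at least one) = 1 − (1 − rate)^440. This counts all 440 subjects as ACAM2000 recipients, which is an upper bound. Rates are from label Tables 1A (primary vaccination, age 20 and over) and 2 (Department of Defense program).
- Generalized vaccinia, 58.86 to 212.1 per million: 0.03 to 0.09 cases; P = 2.6% to 8.9%.
- Inadvertent inoculation, 84.86 to 606.1 per million: 0.04 to 0.27 cases; P = 3.7% to 23.4%.

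No comparison of these complications is possible at this size, whatever the memory aid asks.

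**The case against.** The strongest reply is that rash is not lost. Protocol 8.1.3.1 has the investigator ask about any adverse event at each visit up to Visit 10 (Group 1) or Visit 4 (Group 2). Visits after ACAM2000 fall at days 6-8, 13-15 and 27-29, and the vaccination site is examined at each. More than one lesion is noted in the CRF (7.4). Subjects are told to contact the physician about severe, unexpected reactions (8.2.6). The SAP tabulates pooled solicited and unsolicited events by preferred term. All this stands, so a reader should not infer that rash is recorded only if the subject volunteers it. What remains is that the question is open rather than specific, and that the targeted examination follows symptoms already identified or reported (8.2.3).

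Nor should a reader infer that lesions would be found late for want of the line. The memory aid is reviewed at the day 6-8 and 13-15 visits, where the adverse event question is asked anyway.

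The source argument has limits too. The label's checklist also held diarrhea, constipation, vomiting, feeling hot and palpitations, which this trial does not solicit, so choosing among items is the sponsor's right. That is fair, and the omission is not a breach of Protocol 8.1.3.2. Rash is singled out because the appended diary asks about it daily and the vaccines are expected to differ on it.

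Finally, the memory aid form is not among the documents, and the military forms may be completed outside the trial. The memorandum that might settle this is redacted. The trial task lists show no handout of those forms, and the protocol describes no route from them to the CRF.

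**Conclusion.** The point holds as a low-cost improvement to a descriptive secondary endpoint. The likely effect is an undercount of rash: about 24 Group 2 subjects expected at the label rate, and about 12 recorded if half are captured. This assumes that the label rate carries over to this population, that the protocol's list reflects the actual memory aid, and a capture fraction that the documents do not supply.

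Three stronger readings are tempting but unsupported:
- **That a hazardous reaction goes unmonitored.** The label states "Inadvertent inoculation at other body sites is the most frequent complication of vaccinia vaccination", and Protocol 4.5 asks for immediate reporting of "Suspected cases of illnesses such as progressive vaccinia, eczema vaccinatum, and severe generalized vaccinia or inadvertent inoculation". The common rash is a different matter: section 6.1 of the label describes generalized rashes as mostly resolving without treatment. The dangerous forms are too rare to compare here and have their own reporting route.
- **That open-label reporting would create a false group difference.** Counselling on contact spread might seem to prompt ACAM2000 recipients more, but Visits 1 to 4 list it for both groups, and after ACAM2000 both groups receive it. The documents give no capture rates from which to size any gap.
- **That a planned test loses power.** SAP 3.10.9 plans Fisher tests for any treatment-emergent event and any serious event, not for rash. Protocol 9.6 treats secondary tests as descriptive.

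**What to change.** Add one daily Yes/No line with location to the memory aid, after every vaccination and in both groups: *rash or vaccine-type lesion anywhere other than the vaccination site*. Swollen lymph nodes are already recorded as Yes/No in Protocol Table 3, so the format has a precedent.

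Add the item to the solicited general events in Protocol 8.1.3.2, 8.2.6.2 and 9.3.2 (with the synopsis) and in SAP 1.4.4 and 3.9.2. Tabulate it per vaccination with the other solicited general events. If vaccination has already begun when the change is made, report the item by memory-aid version.

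The cost is one diary line, one CRF field and one table row. Diary completion takes slightly longer, and more mild rashes will be recorded.

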**Use all the letter codes that apply to describe vaccination site for each day above:**

- 1= red spot    2= bump    3=reddish blister    4=whitish blister    5=scab  
 6=ulcer, crater    w=warmth    sw=swollen>3 in.    st=streaks    dr=drainage

If medical care sought, where? Name of facility/MD: \_\_\_\_\_

**Permission to acquire medical records?**  Yes  No

Additional comments (use additional pages if necessary): \_\_\_\_\_

Signature of vaccinee: _____	Date completed: _____
------------------------------	-----------------------

DATA PRIVACY NOTICE: Data requested are being collected under the authority of The Privacy Act of 1974, 5 U.S.C. §552A. The SSN is being collected because it is a unique identifier that will better enable military staff to maintain contact with patients over time. Every effort will be made to safeguard the confidentiality of the information provided.

## **17.9 Appendix IVe: Attachment 5 to US Health Affairs Memorandum 'Smallpox Vaccine in Pregnancy Registry, Information Paper'**

Note: The US Health Affairs Memorandum; Update of Clinical Policy for the Department of Defense Smallpox Vaccination Program attaches the 'Smallpox Vaccine in Pregnancy Registry, Information Paper' from September 2007. This CTP replaces this paper with the latest version from 26-June-2012.

## VACCINATION-RESPONSE INTERPRETATION

**Inspect the vaccination site 6 to 8 days after vaccination.** Interpret the response at that time. The World Health Organization (WHO) Expert Committee on Smallpox defined two types of responses:

- a) major reaction: virus replication took place and vaccination was successful; or
- b) equivocal reaction: a possible consequence of immunity adequate to suppress viral multiplication or allergic reactions to an inactive vaccine without production of immunity.

### **Major Reaction:**

A vesicular (blister) or pustular (pus-filled) lesion or area of definite palpable induration or congestion surrounding a central lesion that might be a crust or an ulcer.

After primary (first) vaccination, the vaccination site usually progresses as follows:

- The inoculation site becomes reddened and pruritic 3 to 4 days after vaccination.
- A vesicle surrounded by a red areola then forms, which becomes umbilicated (collapsed center) and then pustular by days 7 to 11 after vaccination.
- The pustule begins to dry; the redness subsides; and the lesion becomes crusted between the second and third week. By the end of about the third week, the scab falls off, leaving a permanent scar that at first is pink in color but eventually becomes flesh-colored.
- After revaccination, skin reactions might be less pronounced with more rapid progression and healing than those after primary vaccination. Revaccination is successful if a pustular lesion or area of definite induration or congestion surrounding a central lesion (i.e., scab or ulcer) appears 6 to 8 days after revaccination.

### **Equivocal Reaction:**

Equivocal reactions, including accelerated, modified, vaccinoid, immediate, early, or immune reactions, are all responses other than major reactions. If an equivocal reaction is observed, check vaccination procedures and repeat vaccination using another vial or vaccine lot, if available. A response to smallpox vaccination may be blunted by immunity, insufficiently potent vaccine, or vaccination technique failure. If repeat vaccination using vaccine from another vial fails to elicit a major reaction, consult public-health authorities before attempting another vaccination of that person.

Sources: Fenner et. al, 1988 (pp 296, 312-314); ACIP, 2001.

**17.11 Appendix IVg: Attachment 7 to US Health Affairs Memorandum  
'Policy for Smallpox Vaccine and Persons with Cardiac Conditions'**

(b) (1) (A)

(b) (1) (A)

**17.12 Appendix IVh: Attachment 8 to US Health Affairs Memorandum  
'Establishment of Case Management Guidelines for Smallpox Vaccine  
Associated Myopericarditis'**

(b) (1) (A)

(b) (1) (A)

**17.13 Appendix IVi: Attachment 9 to US Health Affairs Memorandum  
'Information Paper Vaccinia Immune Globulin Intravenous (Human)  
(VIGIV)'**

Note: The US Health Affairs Memorandum; Update of Clinical Policy for the Department of Defense Smallpox Vaccination Program attaches 'Information Paper Intra-Venous Vaccinia Immune Globulin (IV-VIG)' from 9 November 2007. This CTP replaces this Information Paper with the 'Information Paper Vaccinia Immune Globulin Intravenous (Human) (VIGIV)' dated 25 June 2013.

